## 15.0 Drug Information

### 15.1 Ibrutinib (ImbruvicaTM, PCI-32765)

15.11 **Background:** Ibrutinib is an antineoplastic agent that is an inhibitor of Bruton's tyrosine kinase.

15.12 **Formulation:** Ibrutinib comes in a different dosage forms.

- Capsules: either size 0, gray 140 mg capsules or size 2, yellow immediate-release 70 mg capsules. The capsules also contain the following compendial excipients: microcrystalline cellulose, croscarmellose sodium, sodium lauryl sulfate, and magnesium stearate. Capsules are packaged in high-density polyethylene bottles with an induction seal and a child resistant screw-top cap.

15.13 **Preparation and storage:**

- Ibrutinib capsules: 70 mg and 140 mg. store at 15°C to 25°C (59°F to 77°F) with excursions permitted to 30°C (86°F).

15.14 **Administration:** Administer orally with water at approximately the same time every day. Ibrutinib can be taken with or without food. Swallow capsules whole; do not open, break, or chew the capsules. Hazardous agent; use appropriate precautions for handling and disposal.

15.15 **Pharmacokinetic information:**

a) Absorption – Current data indicates bioavailability is low and displays high inter-subject variability. The median time to reach maximum plasma concentration ( $T_{max}$ ) is approximately 2 hours. Administration of ibrutinib in a fasted condition resulted in approximately 60% of exposure as compared to administration either in fed condition (30 minutes after a high-fat breakfast), or when drug was taken 30 minutes before or 2 hours after a meal. Based on data for the effects of food, ibrutinib could be taken with or without food at approximately the same time each day. The effect of food on the PK of ibrutinib 560 mg tablets was similar to that observed for ibrutinib capsules.

b) Distribution: The plasma protein binding of ibrutinib and its metabolite PCI 45227 in human plasma is 97.3% and 91%, respectively. The apparent steady state volume of distribution is approximately 10,000 L.

c) Metabolism – Ibrutinib is extensively metabolized by CYP3A4/5 (major) and CYP2D6 (minor). Ibrutinib is metabolized in the liver.

d) Elimination – The excretion of ibrutinib is predominantly via the feces with approximately 80% recovered mostly within 2 days, whereas ~8% is excreted in urine. Approximately 1% of the ibrutinib is recovered as unchanged drug, all in feces. The half-life elimination is 4-6 hours. Overall, these PK characteristics resulted in minimal accumulation of both parent compound and metabolite PCI-45227 on repeated daily dosing of ibrutinib.

e) Special populations: a small increase in bioavailability was estimated with increasing age. Exposure is predicted to increase approximately 14% and decrease approximately 20% in subjects of 81 and 49 years of age, compared to a typical 67-year old subject. No statistically significant

effects were observed for the other covariates tested, i.e., sex, race, mild and moderate renal impairment, mild hepatic impairment and B-cell histology. The recommended doses for patients with mild and moderate liver impairment are 280 mg/day and 140 mg/day (Child-Pugh Class A and B, respectively). It is not recommended to administer ibrutinib to subjects with severe hepatic impairment (Child-Pugh Class C). Pediatric studies are still ongoing.

**15.16 Potential Drug Interactions:** Ibrutinib is primarily metabolized by cytochrome P450 enzyme 3A4/5. Voriconazole and posaconazole can be used concomitantly with ibrutinib as per the dosing guidance described in the specific clinical study protocol. All other strong inhibitors of CYP3A (eg, ketoconazole, indinavir, nelfinavir, ritonavir, saquinavir, clarithromycin, telithromycin, itraconazole, nefazodone, and cobicistat) should be avoided, and an alternative with less CYP3A inhibitory potential should be considered. If the benefit outweighs the risk and a strong CYP3A inhibitor must be used, see the recommended dose modifications described in the specific clinical study protocol.

If a moderate CYP3A inhibitor (eg, fluconazole, erythromycin, amprenavir, aprepitant, atazanavir, ciprofloxacin, crizotinib, diltiazem, fosamprenavir, imatinib, verapamil, amiodarone, dronedarone) is indicated in patients with B-cell malignancies, reduce the ibrutinib dose to 280 mg for the duration of the inhibitor use or as per recommended dose modifications described in the specific clinical study protocol. No ibrutinib dose modifications for moderate inhibitors are required in patients with cGVHD dosed with ibrutinib 420 mg.

No dose adjustment is required in combination with mild inhibitors. Monitor patient closely for toxicity and follow dose modification guidance as needed. Avoid grapefruit and Seville oranges during ibrutinib treatment as these contain moderate inhibitors of CYP3A.

Administration of ibrutinib with strong inducers of CYP3A decreases ibrutinib plasma concentrations by up to 90%. Avoid concomitant use of strong CYP3A inducers (eg, carbamazepine, rifampin, phenytoin and St. John's Wort). Consider alternative agents with less CYP3A induction.

To minimize the potential for an interaction in the GI tract, narrow therapeutic range P-gp or BCRP substrates such as digoxin or methotrexate should be taken at least 6 hours before or after ibrutinib. Ibrutinib may also inhibit BCRP systemically and increase the exposure of drugs that undergo BCRP-mediated hepatic efflux, such as rosuvastatin.

There have been reports of bleeding-related events in subjects treated with ibrutinib. Warfarin or other vitamin K antagonists should not be administered concomitantly with ibrutinib unless specified in the protocol. Supplements such as fish oil and vitamin E preparations should be avoided.

Based on preliminary data from the combination studies of ibrutinib and venetoclax, venetoclax exposure (area under the concentration-time curve [AUC]) at 400 mg QD appears to be approximately 1.7 to 1.8-fold higher with 420 mg ibrutinib and approximately 3-fold higher with 560 mg compared with venetoclax single agent exposure. To date, no new safety signals have been identified in these ongoing combination therapy studies. Patients should be closely monitored for signs of toxicity.

Evaluation of the effect of repeated administration of ibrutinib on the PK of oral contraceptives (OC), showed that the maximal daily dose of 560 mg did not lead to a decreased exposure of OC drugs ethinylestradiol(EE)/levonorgestrel in female subjects, suggesting that the OCs remain efficacious when used during ibrutinib therapy.

#### 15.17 Known potential toxicities:

- **Very Common (≥10%):** neutropenia, thrombocytopenia, anemia, diarrhea, nausea, constipation, vomiting, decreased appetite, fatigue, peripheral edema, pyrexia, pneumonia, upper respiratory tract infection, arthralgia, back pain, headache, cough, dyspnea, rash
- **Common (1 to <10%):** febrile neutropenia, leukocytosis, lymphocytosis, atrial fibrillation, vision blurred, stomatitis, gastritis, asthenia, bronchitis, lung infection, sinusitis, urinary tract infection, neutrophil count decreased, platelet count decreased, dehydration, hyperuricemia, myalgia, extremity pain, dizziness, hematuria, epistaxis, erythematous rash, maculo-papular rash, hematoma, hypertension, cellulitis, infection, lower respiratory tract infection, sepsis, skin infection, arthritis, bone pain, flank pain, basil cell carcinoma, squamous cell carcinoma, syncope, acute kidney injury, pleural effusion, respiratory failure, macular rash, hypotension, respiratory tract infection, cardiac failure
- **Rare (<1%):** leukostasis syndrome, pancytopenia, atrial flutter, myocardial infarction, colitis, intestinal obstruction, oral mucosal blistering, systemic inflammatory response syndrome, atypical pneumonia, bacteremia, infectious enterocolitis, neutropenic sepsis, periorbital cellulitis, pneumonia (pneumocystis jirovecii, bacterial, cryptococcal, fungal, haemophilus, influenza, viral, pseudomonal klebsiella, legionella, parainfluenzae viral, streptococcal, organising), septic shock, urosepsis, post procedural hemorrhage, subdural hematoma, tumor lysis syndrome, pain (pelvic, groin), hemorrhage intracranial, lung infiltration, pneumonitis, pustular rash, breast cellulitis, bronchopulmonary aspergillosis, Escherichia sepsis, viral lower respiratory tract infection, pneumococcal sepsis, fungal sinusitis, staphylococcal infection, staphylococcal skin infection, interstitial lung disease, angioedema, hypertensive crisis, chronic sinusitis bacteroides bacteremia, orbital cellulitis, staphylococcal cellulitis, Escherichia bacteremia, alveolitis allergic, Stevens-Johnson syndrome, Haemophilus bacteremia/sepsis, pseudomonal lung infection, bacterial sepsis, herpes zoster disseminated, muscle hemorrhage, cerebral hemorrhage, deep vein thrombosis, squamous cell

carcinoma of the skin, basosquamous carcinoma of the skin, hepatic failure, ventricular tachyarrhythmia, basal cell carcinoma, neutrophilic dermatoses

- **Cardiac Arrhythmias:** Atrial fibrillation, atrial flutter, and cases of ventricular tachyarrhythmia including some fatal events, have been reported in subjects treated with ibrutinib, particularly in subjects with cardiac risk factors, hypertension, acute infections, and a previous history of cardiac arrhythmia. Periodically monitor subjects clinically for cardiac arrhythmia. Subjects who develop arrhythmic symptoms (eg, palpitations, lightheadedness, syncope, chest discomfort or new onset of dyspnea) should be evaluated clinically, and if indicated, have an ECG performed. For cardiac arrhythmias which persist, consider the risks and benefits of ibrutinib treatment, and follow the dose modification guidelines
- **Cerebrovascular accidents:** Cases of cerebrovascular accident, transient ischemic attack, and ischemic stroke including fatalities have been reported with the use of ibrutinib in the post-marketing setting, with and without concomitant atrial fibrillation and/or hypertension. Regular monitoring and appropriate treatment of conditions that can contribute to the occurrence of these events is recommended.

Please refer to the prescribing information or Investigator's Brochure for a more complete comprehensive list of treatment-

15.18 **Drug procurement:** Drug will be provided free of charge to study participants by Pharmacyclics, Inc.

15.19a **Nursing Guidelines:**

- There are numerous drug to drug interactions. Record all of patient's medications including OTC, and herbal use. Avoid concomitant use with agents as listed in section 15.16.
- Patients should be instructed to avoid eating grapefruit (including juice) and Seville oranges while on ibrutinib.
- Peripheral edema is common. Instruct patients to report this to the study team.
- Gastrointestinal side effects are common (diarrhea, nausea, constipation, abdominal pain, vomiting, etc). Treat symptomatically and monitor for effectiveness of intervention.
- Monitor CBC w/diff. Instruct patients in energy conserving lifestyle (anemia) and to report any unusual bruising or bleeding and/or signs or symptoms of infection to study team.
- Arthralgias, Myalgias, and muscle spasm can be seen. Treat symptomatically and monitor for effectiveness.
- Monitor renal function/uric acid levels, especially in patients who may be experiencing dehydration.
- Respiratory symptoms may include, cough, SOB, and URI. Instruct patients to report these symptoms to the study team.
- Rarely patients can experience secondary skin cancers. Instruct patients to report any new skin lesions to the study team.

- Rash can be seen. Instruct patient to report to study team.
- Cardiac arrhythmias have been seen with this agent including a-fib, atrial flutter and ventricular tachyarrhythmia's, some of which have led to death. Instruct patients who experience any palpitations, lightheadedness, syncope, or SOB to see medical care immediately. This is especially important in patients who have pre-existing cardiac issues.
- Warn patients of the risk of bleeding. Patients should not take warfarin or other vitamin K antagonists while on ibrutinib, unless the protocol allows for it. Additionally, patients should be cautioned to avoid fish oil and vitamin E supplements.
- Patients who are concurrently on ibrutinib and ventoclax should be monitored closely for excess toxicity.
- Ibrutinib should be held at least 3-7 days pre and post-surgery, depending on type of surgery.
- There have been reports of CVA and TIA in patients on ibrutinib. Instruct patients to report any headaches and/or neurologic changes immediately or seek out emergency care.
- Patients may experience dry eyes, blurred vision or decreases in vision. Instruct patients to report this to the study team.

#### 15.19b Medications to be Used with Caution with Ibrutinib

##### CYP3A-Inhibitors/Inducers

Ibrutinib is metabolized primarily by CYP3A. Avoid co-administration with strong CYP3A4 or moderate CYP3A inhibitors and consider alternative agents with less CYP3A inhibition.

- If a strong CYP3A inhibitor (eg, ketoconazole, indinavir, nelfinavir, ritonavir, saquinavir, clarithromycin, telithromycin, itraconazole, nefazadone, or cobicistat) must be used, reduce ibrutinib dose to 140 mg or withhold treatment for the duration of inhibitor use. Subjects should be monitored for signs of ibrutinib toxicity.
- If a moderate CYP3A inhibitor (eg, voriconazole, erythromycin, amprenavir, aprepitant, atazanavir, ciprofloxacin, crizotinib, darunavir/ritonavir, diltiazem, fluconazole, fosamprenavir, imatinib, verapamil, amiodarone, or dronedarone) must be used, reduce ibrutinib to 140 mg (for 840 mg/day dose, reduce to 280 mg) for the duration of the inhibitor use. Avoid grapefruit and Seville oranges during ibrutinib/placebo treatment, as these contain moderate inhibitors of CYP3A.
- No dose adjustment is required in combination with mild inhibitors.

Avoid concomitant use of strong CYP3A inducers (eg, carbamazepine, rifampin, phenytoin, and St. John's Wort). Consider alternative agents with less CYP3A induction.

A list of common CYP3A inhibitors and inducers is provided in Appendix 10. A comprehensive list of inhibitors, inducers, and substrates may be found at

<http://medicine.iupui.edu/clinpharm/ddis/main-table/>. This website is continually revised and should be checked frequently for updates.

For the most comprehensive effect of CYP3A inhibitors or inducers on ibrutinib exposure, please refer to the current version of the IB.

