**EXCEPTIONS:**

- Adequately treated basal cell or squamous cell skin cancer
- Any *in situ* cancer
- Adequately treated Stage I or II cancer from which the patient is currently in complete remission, or
- Any other cancer from which the patient has been disease-free for  $\geq$ at least three years prior to registration

3.25 Concurrent therapy considered to be investigational.

**NOTE:** Patients must not be planning to receive any radiation therapy (except localized radiation for palliative care that must be completed prior to starting Cycle 1, Day 1).

3.26 Any of the following because this study involves an investigational agent whose genotoxic, mutagenic and teratogenic effects on the developing fetus and newborn are unknown:

- Pregnant women
- Nursing women (lactating females are eligible provided that they agree not to breast feed while taking lenalidomide)
- Men or women of childbearing potential who are unwilling to employ adequate contraception

3.27 Requires treatment with a strong cytochrome (CYP) 3A4/5 inhibitor (as outlined in Appendix X).

3.28 Major surgery  $\leq$ 4 weeks prior to registration.

3.29a History of stroke/intracranial hemorrhage  $\leq$ 6 months prior to registration.

3.29b Requires use of therapeutic anticoagulation prior to registration  
**NOTE:** thromboprophylaxis with any agent is permitted.

3.29c History of clinically significant bleeding or known platelet or coagulation disorder.

3.29d Clinically significant cardiac illness including New York Heart Association (NYHA) Class III or Class IV heart failure (Appendix VI), unstable angina pectoris, myocardial infarction within the past 6 months, or  $\geq$ Grade 3 cardiac arrhythmias noted  $\leq$ 14 days prior to registration.

3.29e Hepatic impairment

3.29e1 Phase I  
Any currently active, clinically significant hepatic impairment (Child-Pugh class A, B, or C according to the Child Pugh classification see Appendix XII).

3.29e2 Phase II  
Currently active, clinically significant hepatic impairment Child-Pugh class B or C according to the Child Pugh classification (see Appendix XII).

3.29f Known HIV+ patients  
EXCEPTION: If they meet the following additional criteria  $\leq$ 28 days prior to registration:

- CD4 cells  $\geq$ 500/mm^3
- Viral load of <50 copies HIV mRNA/mm^3 if on cART or <10,000 copies HIV mRNA if not on cART
- No zidovudine or stavudine as part of cART

3.29g Known Hepatitis B or Hepatitis C infection  

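### Protocol Sections 15.16 and 15.19b print ibrutinib doses that differ twofold for the same moderate CYP3A inhibitor at every dose level below 840 mg, and no text says which section governs

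*Combined protocol and SAP*

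**What the plan says.** Protocol Section 15.16 (potential drug interactions) covers moderate CYP3A inhibitors in patients with B-cell malignancies, a group in which Section 1.5 includes myeloma by its heading. The instruction is to "reduce the ibrutinib dose to 280 mg for the duration of the inhibitor use", followed by an alternative: "or as per recommended dose modifications described in the specific clinical study protocol".

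Section 15.19b (medications to be used with caution) first advises against giving strong or moderate inhibitors with ibrutinib. It then says that if a moderate inhibitor "must be used, reduce ibrutinib to 140 mg (for 840 mg/day dose, reduce to 280 mg", closing the bracket there. For a strong inhibitor that cannot be avoided, the same section says to "reduce ibrutinib dose to 140 mg or withhold treatment for the duration of inhibitor use".

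On class, Section 15.16 says "Voriconazole and posaconazole can be used concomitantly with ibrutinib as per the dosing guidance described in the specific clinical study protocol", and its next sentence opens "All other strong inhibitors of CYP3A". Section 15.19b and Appendix X both put voriconazole among the moderate inhibitors. Appendix X puts posaconazole among the strong ones.

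Exclusion criterion 3.27 reads "Requires treatment with a strong cytochrome (CYP) 3A4/5 inhibitor (as outlined in Appendix X", with the bracket closing there. It covers strong inhibitors only.

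**The concern.** Both instructions sit in the drug-information section of the one document that sites work from, and they attach different ibrutinib doses to the same co-medication. The clause in 15.16 that defers to the study protocol does not settle the matter by itself, because this document is the study protocol and both figures are in it.

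Criterion 3.27 does not bar moderate inhibitors, so a patient already taking one can enrol and the conflict can apply from the first day of treatment. The dose the patient then receives could depend on which page the site opens. That is a patient-safety matter, and it also affects what the dosing record means.

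**Working it through.** No sample size, power or error rate is involved. The check sets the two rules side by side at each ibrutinib dose in the trial.

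**Inputs**
- Ibrutinib doses: 280, 420, 560, 700 and 840 mg, with 420 mg as the starting level (Section 7.31; the same doses appear in Section 8.223).
- Rule A (15.16): 280 mg whatever the current dose, or the modification in the study protocol.
- Rule B (15.19b): 280 mg if the dose is 840 mg/day, otherwise 140 mg.

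**Do the rules cover the same drugs?** Section 15.16 names 13 moderate inhibitors: fluconazole, erythromycin, amprenavir, aprepitant, atazanavir, ciprofloxacin, crizotinib, diltiazem, fosamprenavir, imatinib, verapamil, amiodarone and dronedarone. All 13 are in the 15.19b list, which adds voriconazole and darunavir/ritonavir. Every moderate inhibitor that 15.16 names therefore falls under both rules.

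**Size of the difference.** Ratio = dose under A / dose under B. Cut = 1 − (new dose / current dose).

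| Current dose (mg/day) | Rule A (15.16), mg | Rule B (15.19b), mg | Ratio A/B | Cut under A | Cut under B |
|---|---|---|---|---|---|
| 280 | 280 | 140 | 2.0 | 0% | 50% |
| 420 | 280 | 140 | 2.0 | 33% | 67% |
| 560 | 280 | 140 | 2.0 | 50% | 75% |
| 700 | 280 | 140 | 2.0 | 60% | 80% |
| 840 | 280 | 280 | 1.0 | 67% | 67% |

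For example, at 420 mg: 1 − 280/420 = 33% and 1 − 140/420 = 67%. At 280 mg, the figure in 15.16 is no reduction at all, while 15.19b halves the dose.

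**Does any other text break the tie?** Section 8 has no CYP3A rule. Section 15.19a (nursing guidelines) points staff to 15.16 for the agents to avoid, and Section 9.9a points to Section 15.0 as a whole. Neither gives 15.19b precedence.

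**Side check on voriconazole.** Section 15.16 prints no dose for it, so the only arithmetic is what its class changes under 15.19b:
- At 840 mg/day: 280 mg if moderate; 140 mg or withhold if strong (280/140 = 2).
- At lower doses: 140 mg if moderate; 140 mg or withhold if strong. The dose is the same, with a withhold option added.

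**The case against.** The best defence is that 15.16 does not prescribe 280 mg outright. It reads like a general drug monograph: it mentions chronic graft-versus-host disease and speaks of the study protocol in the third person. Section 15.19b has a line for 840 mg/day, the top level of this trial. On that reading 15.16 hands over to 15.19b and there is one rule.

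This softens the conflict but does not remove it. The clause is an alternative joined by an *or*, so 280 mg remains a printed option that 15.19b does not allow below 840 mg/day. Nor is 15.19b plainly the tailored text: it refers to placebo, which this open-label, non-randomized trial does not have.

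Two safeguards also stand. Section 15.19b says to avoid these inhibitors and consider alternatives first. Footnote j of Section 4.1 requires a medication review before every cycle. Both limit how often the question arises, but neither answers it.

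Some stronger readings are tempting, and the documents do not support them:
- *That the voriconazole mismatch produces the twofold gap.* Its strong class in 15.16 is implied by "All other strong inhibitors of CYP3A", not stated, and 15.16 gives it no dose. The gap exists for the other moderate inhibitors regardless.
- *That allowing posaconazole in 15.16 contradicts criterion 3.27.* That criterion governs entry, while 15.16 and 15.19b govern use on treatment. Excluding a drug at entry and giving a rule for unavoidable later use are compatible.
- *That dose finding in Phase I is distorted.* At 420 mg and above, either rule takes the patient off the assigned dose, so a departure would remain after reconciliation. The conflict changes its size. No effect on DLT counts or on the MTD can be shown from the documents.
- *That many patients are affected.* The documents give no frequency of use for these co-medications.

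**Conclusion.** The point holds in a narrow form. For a moderate CYP3A inhibitor, Sections 15.16 and 15.19b print ibrutinib doses that differ by a factor of 2 at four of the five dose levels (280, 420, 560 and 700 mg) and agree at 840 mg, with no stated precedence. The voriconazole class is a secondary inconsistency.

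The conclusion assumes that the 840 mg/day exception in 15.19b refers to the dose the patient is taking when the inhibitor starts. The factor of 2 is a ratio of prescribed doses, not of drug exposure, since the documents give no exposure figure for moderate inhibitors. The number of patients affected is unknown. If Phase II ran at 840 mg, the moderate-inhibitor doses would agree for patients still on that dose; at any lower Phase II dose the conflict would apply.

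**What to change.** The sponsor should reconcile Sections 15.16 and 15.19b and Appendix X, preferably in one table that puts each inhibitor in a single class with a single ibrutinib action for each current dose. The voriconazole class should be settled in the same table. Section 15.16 should then either carry that rule or refer by number to the section that does, in place of its general reference to a study protocol. One sentence should state which section governs, and the cross-reference in 15.19a should point there.

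The choice of dose and class belongs to the sponsor and its clinical pharmacology advisers; nothing here favours either figure. The cost is a wording amendment and notice to sites. Sample size, endpoints and analysis do not change.
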